When using a cannula: after each blood sample, the cannula will be flushed with 3 to 5 mL normal saline, to keep it patent. In order to minimise dilution of each subsequent blood sample with normal saline, the following procedure will be used: about 1 mL will be drawn via the cannula into the sampling syringe and discarded. The definitive blood sample will then be collected.

Appendix 4. Total Blood Volume to be Collected in Part 2

The blood volume planned to be collected from each subject during Part 2 of the study is detailed in Table 10, rounded up to the nearest 1 mL. Additional samples may be required in the event of AEs. The total blood volume to be taken during the study will be confirmed once the regimens for Part 2 have been selected.

Table 10. Total Blood Volume in Part 2 - Phase II

Test	Planned	Volume (mL)	Total planned
	number of tests		blood volume (mL)
Pregnancy serum test	2	Screening and Day	0
		13:0 (on biochemistry	
		tube)	
Parasitology - microscopy	1	4	5
Parasitology - RDT		1	
Haematology	4	4	16
Biochemistry	4	5	20
Pharmacokinetics	10	1	10
Exploratory samples	5	5	25
Cannula discard	7	1	7
Total blood volume to	84		

RDT: rapid diagnostic test

When using a cannula: after each blood sample, the cannula will be flushed with 3 to 5 mL normal saline, to keep it patent. In order to minimise dilution of each subsequent blood sample with normal saline, the following procedure will be used: about 1 mL will be drawn via the cannula into the sampling syringe and discarded. The definitive blood sample will then be collected.

Appendix 5. Laboratory Analyses

Detailed information about the collection, processing, storage and shipment of the samples will be provided in the laboratory manual and/or Study Operations Manual. Information on the parameters to be analysed and the laboratories to be used is presented in Table 11.

Table 11. Parameters of Laboratory Analyses

Parameters (by category)	Sample destination
Haematology:	Study Investigational sites
haemoglobin, haematocrit, platelets, white blood cells	
(WBC) and differential, red blood cells (RBC).	
Biochemistry:	Study Investigational sites
aspartate transaminase (AST), alanine transaminase (ALT),	
alkaline phosphatase (AP), glucose, creatinine, eGFR, blood	
urea nitrogen (BUN), total bilirubin, albumin, total protein,	
chloride, sodium, potassium and calcium in serum.	
Urinalysis – dipstick, multistick and microscopy:	Study Investigational sites
glucose, ketone bodies, specific gravity, occult blood, pH,	
proteins, leucocytes, bilirubin, urobilinogen, nitrite	
Parasitological co-infections (microscopy):	Study Investigational sites
Blood: lymphatic filariasis, Mansonella perstans, and	
Loa loa	
Urine drug screen:	Study Investigational sites
Drugs of abuse screen	
Serum pregnancy test:	Study Investigational sites
Beta-HCG	
Urine pregnancy test:	Study Investigational sites and Participants'
Beta-HCG	communities
Alcohol test:	Study Investigational sites
Breath test	An All IV. C. 1 D.
Pharmacokinetic analyses in blood:	Attn: AbbVie Sample Receiving
Parameters are specified in Section 5.6	Dalissams Campiana
	Delivery Services [name]
	[name]
	E-mail: [contact]
Microfilarial density from skin snips	Study Investigational sites
O. volvulus	Stady Investigational Sites
Mansonella streptocerca	
Nodule assessment	Institute of Medical Microbiology,
	Immunology and Parasitology; University
	Hospital Bonn, Germany
Exploratory samples	Study Investigational sites
Plasma	May be transferred for logistical purposes
Urine	(longer term storage) to another location with
Remaining samples from those collected from scheduled	prior agreement of Ethical Committees and
protocol procedures	Regulatory Authority.

Appendix 6. Adverse Event Severity Grading Reporting for DNDi-TYL-01 Clinical Trial

Please refer to most current document "Adverse Event Severity Grading Reporting for DNDi-TYL-01" attached to the protocol.

Appendix 7. Permitted and non-permitted birth control methods in DNDi-TYL-01

Permitted birth control methods in DNDI-TYL-01

Methods which may be considered as "highly effective" (failure rate of less than 1% per year when used consistently and correctly):

(based on the Clinical Trial Facilitation Group recommendations from The Medicines and Healthcare Products Regulatory Agency website related to contraception and pregnancy testing in clinical trials, dated 15 September 2014).

- Combined (oestrogen and progestogen containing) hormonal contraception associated with inhibition of ovulation:
 - oral
 - · intravaginal
 - · transdermal
- Progestogen-only hormonal contraception associated with inhibition of ovulation:
 - oral
 - injectable
 - implantable
- intrauterine device (IUD)
- intrauterine hormone-releasing system (IUS)
- bilateral tubal occlusion
- vasectomised partner¹
- sexual abstinence²

¹ Vasectomised partner is a highly effective birth control method provided the partner is the sole sexual partner of the WOCBP and that the vasectomised partner has received medical assessment of the surgical success.

² In the context of this guidance sexual abstinence is considered a highly effective method only if defined as refraining from heterosexual intercourse during the entire period of risk associated with the study treatments. The reliability of sexual abstinence needs to be evaluated in relation to the duration of the clinical trial and the preferred and usual lifestyle of the subject.

Non-Permitted birth control methods in DNDI-TYL-01

- Progestogen-only oral hormonal contraception, where inhibition of ovulation is not the primary mode of action
- male or female condom with or without spermicide¹
- cap, diaphragm or sponge with spermicide¹
- Periodic abstinence (calendar, symptothermal, post-ovulation methods), withdrawal (coitus interruptus), spermicides only, and lactational amenorrhoea method are not acceptable methods of contraception. Female condom and male condom should not be used together.

¹ A combination of male condom with either cap, diaphragm or sponge with spermicide (double barrier methods) are not considered highly effective birth control methods and therefore are not permitted in DNDI-TYL-01.

Appendix 8. Prohibited medications in DNDi-TYL-01

I. Prohibited medication before starting the study (see also Section 6.2)

- within 2 years prior to start of IMP administration: moxidectin;
- within 1 year prior to start of IMP administration: more than 2-week course of anti-Wolbachia treatments, i.e. doxycycline, minocycline, rifapentine or rifampicin;
- within 6 months prior to start of IMP administration: ivermectin;
- within 3 months prior to start of Screening (or within 5 times the half-life of the drug tested): any investigational drug;
- within 4 weeks prior to start of IMP administration: any vaccination;
- Within 14 days prior to start of IMP administration:
 - o any medication (with the exception of diclofenac, paracetamol, ibuprofen and aspirin), herbal preparation or food supplement;
 - o strong CYP3A inhibitors or inducers including but not limited to ritonavir^c, ketoconazole^c, rifampicin, phenytoin, phenobarbital, carbamazepine, cimetidine^c (or within 10 half-lives, whichever is longer);
 - o other drugs known to interact with albendazole such as praziquantel^c, theophylline^c or dexamethasone^c (or within 10 half-lives, whichever is longer);

II. Prohibited medication throughout the entire study^a

Prohibited medication throughout the entire study include any medication that may have an impact on the study objective. Specifically, medication with anti-filarial or anti-Wolbachia effects are prohibited, including:

- ivermectin, excluding post-study ivermectin or rescue ivermectin as detailed in Section 8.3.
- moxidectin,
- doxycycline,
- minocycline,
- rifampicin,
- rifapentine.

III. Prohibited medications during the first 28 days after the last IMP administration

Albendazole (however it is permitted thereafter, one dose per year in MDA)

IV. Prohibited medication during the treatment period

Up to 24 hours after the final dose of IMP, medication, herbal remedies or food supplements, that could affect the PK and/or PD of ABBV-4083 and/or albendazole are prohibited.

- Any CYP3A and/or P-gp inhibitors or inducers, such as:
 - o ritonavirc,
 - o ketoconazolec,
 - o rifampicin^b,
 - o phenytoin^b,
 - phenobarbital^b,
 - carbamazepine^b,
 - o cimetidinec,
 - o others known to interfere with the CYP3A and/or P-gp metabolic pathways (the US FDA tables of Substrates, Inhibitors and Inducers^b will be used as a reference, and included in the Study Operations Manual for reference).
- Drugs known to interact with albendazole, such as
 - o praziquantelo,
 - o dexamethasone^b
 - o theophylline^c
- a. Subjects taking these medications during the study will not be included in the PP population for analysis and will be imputed as failures in analyses of the primary and secondary endpoints in the ITT population.
- b. Subjects taking these medications during the treatment period (or for 14 days before) will not be included the PP population for analysis but will not be imputed as failures in analyses of the primary and secondary endpoints in the ITT population.
- c. Subjects taking these medications during the treatment period (or for 14 days before) will be included in the PP population for analysis and will not be imputed as failures in analyses of the primary and secondary endpoints in the ITT population.

# 1.0 Introduction

This Statistical Analysis Plan (SAP) describes the statistical analyses of Part 1 only for ABBV-4083 Study B18-894/DNDi-TYL-01 "A Phase-II, Randomised, Double-blind, Parallel-group, Proof-of-concept Trial to investigate ABBV-4083 given for 7 or 14 Days or in combination with Albendazole in Subjects with *Onchocerca volvulus* Infection." Part 2 will have a separate clinical database with a separate SAP and database lock.

Part 1 of Study B18-894/DNDi-TYL-01 investigates the safety, tolerability, efficacy for duration-ranging and pharmacokinetics of ABBV-4083 with or without albendazole in subjects infected with *Onchocerca volvulus*.

The analyses of pharmacokinetic endpoints and their relationship to efficacy and safety endpoints will not be covered in this SAP.

The SAP will not be updated in case of administrative changes or amendments to the protocol unless the changes impact the analysis.

Unless noted otherwise, all analyses will be performed using SAS Version 9.4 (SAS Institute Inc., Cary, NC 27513) or later under the UNIX operating system.

All analyses in this SAP are consistent with what is described in the study protocol unless otherwise noted in Section 13.0.

complete treatment, did not have Month 6 nodulectomy data, or took prohibited medications will be excluded.

#### 2.2 Study Design Overview

A total of 150 subjects will be enrolled into five treatment arms with 30 subjects for each arm. The treatment period will last for 14 days and the post-treatment period will follow till Month 6. Post-study ivermectin that kills microfilaria will be given to all participants after nodulectomy at Month 6.

The schematic of the study is shown in Figure 1.

#### Figure 1. Study Schematic

4083 = ABBV-4083; Alb = albendazole; d = days; D = (study) day; IVM = ivermectin; M = month; Pbo = placebo

#### 2.3 Treatment Assignment and Blinding

Subjects will be randomized continuously 1:1:1:1:1 into one of five parallel treatment arms through an Interactive Response Technology (IRT) system. Randomization will be

stratified by the number of operable sites with onchocercomata (one site vs. more than one site).

The five treatment arms are defined as follows:

- Arm A: 7 days of ABBV-4083 400 mg + albendazole matching placebo followed by 7 days of ABBV-4083 matching placebo
- Arm B: 7 days of ABBV-4083 400 mg + albendazole matching placebo followed by 7 days of ABBV-4083 400 mg
- Arm C: 7 days of ABBV-4083 400 mg + albendazole 400 mg followed by 7 days of ABBV-4083 matching placebo
- Arm D: 3 days of ABBV-4083 400 mg + albendazole 400 mg followed by 4 days of ABBV-4083 400 mg + albendazole matching placebo followed by 7 days of ABBV-4083 matching placebo
- Arm E: 7 days of ABBV-4083 matching placebo + albendazole 400 mg followed by 7 days of ABBV-4083 matching placebo

The treatment assignment will remain blinded to the Investigator, as well as clinical, pharmacy, and laboratory personnel, and the Sponsor, including statistics and data management personnel and the study monitor, until the final database lock, after all Part 1 subjects are followed to Month 6 or have prematurely discontinued from follow-up.

Toxicity of the treatments will be monitored throughout the study. If > 10% of the subjects in any arm meet any of the protocol-specified toxicity criteria after 15 subjects are enrolled in each arm, the Data and Safety Monitoring Board (DSMB) may recommend halting enrolment into arms of the same or longer duration with or without albendazole and continuing enrolment in those arms of the shorter duration. The enrolment of the closed arms may be reopened using a lower dose of ABBV-4083 at 300 mg QD with the same duration and same combination (with or without albendazole) as the original arm, in which case enrolment will continue until 30 subjects have been enrolled at that dose. However, subjects who have already received 400 mg QD ABBV-4083 in the halted arm

and have not experienced dose-limiting toxicity will be kept on the same dose until treatment completion.

If Arm A, B, C, or D is closed and then reopened using ABBV-4083 at 300 mg QD, the subjects previously given ABBV-4083 at 400 mg QD in the closed arm will be excluded from all efficacy analyses (Section 9.1). Throughout this SAP, Arm A, B, C, D will be used to denote treatment regimens using either ABBV-4083 at 400 mg or 300 mg QD. For the actual treatment assignment, Arm A, B, C, D will be renamed as Arm F, G, H, I, respectively, upon reopening. For safety analyses, all arms will be summarized separately, even if any of them is closed during the study (Section 10.0). If all of Arms A, B, C, and D are closed, and any of Arms F, G, H, I are opened, the control arm (albendazole alone), Arm E, will be replaced with Arm J which uses the same pill count as Arms F, G, H, I to maintain blinding of the control arm. For all analyses, subjects from Arm E and Arm J will be combined.

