3.5.2.3 Dose-adjusted Arms in the Event of Toxicity

If > 10% of subjects in an arm of Part 1 meet any of the toxicity criteria, the actions shown in Table 1 may be implemented. Decisions for dose reduction will be taken based on all available safety data including the events that trigger the dose adjustment process.

Table 1. Dose Adjustment Recommendations for Toxicity Management in Part 1		
Toxicity criteria	Recommended action	Rationale
reached in		

Toxicity criteria	Recommended action	Rationale
reached in		
Arm A or Week 1 of Arm B	Halt all study arms, then begin to enrol new Arm F, Arm G, Arm H and/or Arm I with a reduced dose of ABBV-4083 300 mg QD (n=30/arm), continue to enrol the remainder of Arm E in Arm J (to a total n=30).	Presumes that dose of ABBV-4083 is too high and that albendazole does not add to the observed toxicity.
Week 2 of Arm B	Halt Arm B, then begin to enrol new Arm G with ABBV-4083 300 mg QD (n=30)	Presumes that dosing ABBV-4083 400 mg QD is safe for 7 days but not 14 days.
Arm C	Halt Arm C, then begin to enrol new Arm H with ABBV-4083 300 mg QD (n=30)	Presumes that dosing ABBV-4083 + albendazole 400/400 mg QD is safe for 3 days but not 7 days.
Arm D	Halt Arms C and D, then begin to enrol new Arms H and I with ABBV-4083 300 mg (n=30/arm)	Presumes that dosing ABBV-4083 + albendazole 400/400 mg QD is not safe.

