7.1 Test Investigational and Reference Medicinal Products

7.1.1 ABBV-4083 and Matching Placebo

The test IMP, i.e. the Sponsor's active compound under investigation in the study, is ABBV-4083, which will be administered alone or in combination with the test IMP albendazole.

The composition of the capsule of ABBV-4083 and matching placebo are shown in Table 2.

Table 2. Composition of ABBV-4083 and Matching Placebo

Generic name	ABBV-4083	Matching placebo
Dosage form	Capsule for oral administration	Capsule for oral administration
Dosage strength	100 mg	Not applicable
Composition	Contents: microcrystalline cellulose, dibasic calcium phosphate anhydrous, croscarmellose sodium, hydroxypropyl cellulose, colloidal silicon dioxide, magnesium stearate Capsule: light grey, opaque Capsule shell: gelatine, titanium dioxide, iron oxide black	Contents: microcrystalline cellulose Capsule: light grey, opaque Capsule shell: gelatine, titanium dioxide, iron oxide black

In Part 1, ABBV-4083 will be administered at the dose of 400 mg, i.e. four 100-mg capsules. If toxicity criteria are met (see Section 3.5.2), the dose of ABBV-4083 may be reduced to 300 mg, i.e. three 100-mg capsules, or matching placebo.

The dose(s) of ABBV-4083 in Part 2 will be confirmed based on data from Part 1, i.e. up to two treatment arms from Part 1 that are likely to demonstrate high efficacy at Month 24 and safety will be selected. The choice will take into consideration feasibility to use the regimen as potential future treatment.

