7.3 IMP Assignment and Administration

7.3.1 IMP Assignment and Administration in Part 1

7.3.1.1 IMP Assignment in Part 1

In Part 1, the IMP will be randomly assigned. A total of 150 subjects will be recruited and centrally and continuously randomised under double blind 1:1:1:1:1 into one of five parallel groups (Arms A, B, C, D and E), based on dosing regimen, until group size is achieved. Subjects

will be stratified by the number of operable sites with onchocercomata. There will be two strata, i.e. one site and more than one site.

7.3.1.2 IMP Administration in Part 1

The IMP ABBV-4083 will be administered as 100-mg capsules or matching placebo capsules. The IMP albendazole will be administered as over-encapsulated 400-mg tablets or matching over-encapsulated placebo .

Subjects will receive a maximum of 5 capsules per day for 14 days. Depending on the treatment arm allocation, subjects will receive four ABBV-4083 capsules (400 mg) or matching placebo + one over-encapsulated albendazole tablet (400 mg) or matching placebo, once a day, from Day 0 to Day 6, followed by four ABBV-4083 capsules (400 mg) or matching placebo, once a day, from Day 7 to Day 13.

The IMPs will be administered once daily by the oral route and are to be taken with food (see Section 9.2.8 for details).

The IMP will be administered at the investigational centre at approximately the same time each morning, and intake of the IMP will be directly observed by the study personnel.

7.3.2 IMP Assignment and Administration in Part 2

7.3.2.1 IMP Assignment in Part 2

In Part 2, there will be four treatment arms. The two study arms of the shortest treatment duration in Part 1 that are likely to demonstrate high efficacy at Month 24 (based on Part 1 efficacy results and historical studies with doxycycline) and safety will be selected as active arms for Part 2. In order also to assess an additional effect of a dose of ivermectin at Month 6, participants will be into four groups stratified by the number of operable sites with onchocercomata (one site, > 1 site) and by mean skin mf (≤ 5 mf/mg, > 5 mf/mg) at Screening, with two arms receiving the same ABBV-4083 or ABBV-4083 + albendazole regimen but one receiving ivermectin at Month 6 and the other receiving ivermectin matching placebo.

In the Base Scenario, subjects will be randomly assigned 2:2:2:1 under double blind to Arms K, L, M and N1.

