7.4 Blinding

7.4.1 Blinding Measures

In both parts of the study, the IMPs will be administered under double-blind conditions. To that end, ABBV-4083 and matching placebo capsules, as well as albendazole over-encapsulated tablets or matching placebo capsules will be identical in appearance, i.e. size, shape and colour, taste and smell. In Part 2, over-encapsulated ivermectin tablets and matching placebo capsules will be identical in appearance, taste and smell. The packaging and labelling will be designed to maintain blinding to the Sponsor and study personnel, as well as to subjects. The study data will remain blinded until each planned database locks of the study, and authorisation of data release according to standard operating procedures.

The Investigator, as well as clinical, pharmacy, and laboratory personnel, and the Sponsor, including statistics and data management personnel and the study monitor, will remain blinded during the study, excluding those individuals, intentionally designated as unblinded and described below, so as not to potentially introduce bias, unless safety concerns necessitate unblinding by the Investigator, i.e. if knowledge of the IMP administered is useful for the best medical care of an SAE (see Section 7.4.2).

A copy of the randomisation codes in each part of the study will be kept under the management of dedicated unblinded personnel designated by the Sponsor, and access strictly limited to those minimally designated unblinded staff directly involved in activities requiring access to the randomisation code, e.g. staff directly involved in pharmacovigilance for expedited safety reporting only, bioanalytical processes and PK evaluation, packaging and labelling service providers, etc., plus quality control activities (by independent personnel) related to these activities.

The emergency procedures for revealing medication codes are specified in Section 7.4.2.

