# 6.0 Study Drug Duration and Compliance

For the Safety population, duration of treatment will be summarized by treatment arm and overall. Duration of treatment is defined for each subject as last dosing date minus first dosing date + 1 day. Duration of treatment will be summarized using the number of subjects treated, mean, standard deviation, median, Q1, Q3, minimum, and maximum. In addition, the number and percentage of subjects by each treatment duration interval (1 to 7 days, 8 to 14 days, or > 14 days) will be summarized, and the number and percentage of subjects with duration long enough to meet the Per Protocol definition will also be summarized.

For the Safety population, treatment compliance will be summarized by treatment arm separately for ABBV-4083/matching placebo and albendazole/matching placebo. Treatment compliance is defined as the number of capsules that were taken divided by the number of capsules that should have been taken (56 capsules for 14 days of ABBV-4083/matching placebo at 400 mg QD, 42 capsules for 14 days of

ABBV-4083/matching placebo at 300 mg QD, 7 capsules for 7 days of albendazole/matching placebo). The mean, median, standard deviation, Q1, Q3, minimum, and maximum of treatment compliance will be summarized. In addition, the number and percentage of subjects with treatment compliance between 80% and 120% will also be summarized, excluding subjects with missing values in the denominator. A listing of each subject's treatment compliance will also be provided.

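### If only some Part 1 arms are reopened at 300 mg, their three-capsule daily count sets them apart from the four-capsule arms, and the matched control Arm J does not cover that case

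*SAP*

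**What the plan says.** **Blinding commitment.** Protocol 7.4.1: "In both parts of the study, the IMPs will be administered under double-blind conditions". The measures listed there concern the look, taste and smell of the capsules, and the packaging and labelling. The number of capsules is not mentioned.

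**Capsule number.** Protocol 7.1.1: "In Part 1, ABBV-4083 will be administered at the dose of 400 mg, i.e. four 100-mg capsules". If the toxicity criteria are met, "the dose of ABBV-4083 may be reduced to 300 mg, i.e. three 100-mg capsules, or matching placebo". The compliance denominators in SAP 6.0 are "56 capsules for 14 days of ABBV-4083/matching placebo at 400 mg QD, 42 capsules for 14 days of" the 300 mg regimen, and they count active and placebo capsules together. Protocol 7.3.1.2 describes only the four-capsule case: "subjects will receive four ABBV-4083 capsules (400 mg) or matching placebo", plus one albendazole or placebo capsule on Days 0 to 6. Study personnel watch every intake.

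**Partial reopening.** Protocol Table 1 (3.5.2.3) has four rows. Row 1 halts every arm. Row 2 reads "Halt Arm B, then begin to enrol new Arm G with ABBV-4083 300 mg QD (n=30" per arm). Row 3 replaces Arm C with H. Row 4 replaces Arms C and D with H and I. Under Protocol 3.5.2.2, enrolment may continue in arms that are not halted.

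**The existing safeguard.** SAP 2.3 replaces Arm E by "Arm J which uses the same pill count as Arms F, G, H, I to maintain blinding of the control arm". The condition is that Arms A, B, C and D are all closed and at least one 300 mg arm is opened. Protocol Table 1 likewise uses Arm J only in row 1.

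**The concern.** The SAP's reason for creating Arm J concedes that capsule count can break the blind, yet the remedy is tied to one closure pattern out of four. In the other three, subjects on three capsules are treated in the same centres as subjects on four, under direct observation. No control subject takes three capsules in those patterns, so a three-capsule subject is known to be on active ABBV-4083.

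What is exposed is site judgement. Two of the three toxicity criteria in Protocol 3.5.2.2 depend on the investigator's view of relatedness: related events leading to discontinuation, and related severe or serious events. The same criteria are applied again to the 300 mg arms, and toxicity counts carry forward into Part 2. Stopping IMP (6.5.2) and giving rescue ivermectin (8.3.1) also involve investigator discretion. Investigators sit on the Safety Review Committee (13.2), which is meant to review blinded and to be alerted without learning which arm triggered. Safety and tolerability then feed the choice of regimens for Part 2 (10.9). An arm reopened after a toxicity halt is the one where an unprejudiced safety reading matters most.

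**Working it through.** **1. Reproduce the plan's capsule figures.** Inputs: 100 mg per capsule (Protocol Table 2) and 14 days (SAP 6.0).

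- 400 mg: 400 / 100 = 4 a day; 4 × 14 = 56.
- 300 mg: 300 / 100 = 3 a day; 3 × 14 = 42.

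Both match SAP 6.0 exactly, so the current plan has no fourth, placebo capsule at 300 mg.

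**2. What an observer sees.** Add the albendazole or placebo capsule on Days 0 to 6.

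| | Days 0–6 | Days 7–13 | Course total |
|---|---|---|---|
| 400 mg arms and Arm E | 4 + 1 = 5 | 4 | 56 + 7 = 63 |
| 300 mg arms | 3 + 1 = 4 | 3 | 42 + 7 = 49 |

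**3. Apply this to each row of Table 1.** Each reopened arm enrols 30. Review starts once at least 15 are treated in every arm, so each continuing arm has at most 30 − 15 = 15 left to enrol.

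| Row | Three capsules | Four capsules | Reopened subjects | Most still to enrol on four capsules |
|---|---|---|---|---|
| 1 (all halted) | F, G, H and/or I, with J | none | up to 120 | 0 |
| 2 (Arm B, week 2) | G | A, C, D, E | 30 | 4 × 15 = 60 |
| 3 (Arm C) | H | A, B, D, E | 30 | 4 × 15 = 60 |
| 4 (Arm D) | H, I | A, B, E | 60 | 3 × 15 = 45 |

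In row 1 the count carries no information. In rows 2 to 4 it separates the reopened arm or arms from everything else, including control.

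**4. Which contrasts are touched.** Protocol 10.5 lists six: A, B, C and D each against E, and C and D each against A. Let the reopened arm stand in for the one it replaces.

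- Row 2: one of six (G against E).
- Row 3: two of six (H against E and against A).
- Row 4: four of six (H and I, each against E and A).

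The remaining contrasts are between four-capsule arms and keep their blind as far as count is concerned.

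**5. How likely is a trigger?** The documents give no toxicity rate, so this is a range under assumptions. More than 10% of 15 subjects means at least 2 (1/15 = 6.7%; 2/15 = 13.3%). The chance for one arm at the first look is 1 − (1 − p)^15 − 15p(1 − p)^14.

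| Assumed true rate p | Chance of 2 or more of 15 |
|---|---|
| 1% | 1.0% |
| 2% | 3.5% |
| 5% | 17.1% |
| 10% | 45.1% |

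Reopening also needs a recommendation and a decision, both discretionary, so these are upper figures for one arm at that look.

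**6. Enrolment timing.** Assume equal allocation continues, since no other ratio is given. About 15 subjects of a reopened arm then enrol beside the others, and 30 − 15 = 15 follow after the others have filled. If the trigger came at 20 per arm, the split would be about 10 and 20.

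**The case against.** The arithmetic is not in dispute, but several objections to its reach are fair.

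- A reader might infer that the count always names the arm. It does not. In row 4 three capsules means H or I. In rows 2 and 3 it names G or H only to someone who knows which row was triggered, and the documents do not say that sites are told. Without that knowledge, the count still shows an active 300 mg regimen.
- A reader might infer that the whole double blind fails. The four-capsule arms, control included, cannot be told apart by count. All that is learned about them is that they are not the reopened arm.
- A reader might infer bias in the primary endpoint. Nodules are read by immunohistology at an external university laboratory (Protocol Appendix 5), and nothing shows that it receives capsule counts. The ALT toxicity criterion is a laboratory value.
- The problem depends on a partial trigger and then a reopening, neither of which need occur.
- A placebo top-up cannot blind subjects enrolled after the other arms have filled (step 6), which may be half or more of a reopened arm.

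All five stand and limit the point. They do not remove it. One rescue does not work: the Pharmacy Manual, which is not available here, might specify a top-up capsule, but that would contradict the 42-capsule denominator and leave Arm J without a purpose.

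**Conclusion.** The concern holds in a bounded form. If Part 1 is partly reopened at 300 mg, capsule count shows subjects and site staff who is on an active 300 mg regimen, and the only count-matched control is unavailable in that situation. The size is 30 subjects and one or two contrasts in rows 2 and 3, and 60 subjects and four contrasts in row 4. Site-judged outcomes could be biased: relatedness, discontinuation, rescue, two of the three toxicity criteria, and through them the safety input to Part 2 selection. Neither the direction nor the amount of bias can be derived from the documents.

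The conclusion assumes that the 300 mg regimen is dispensed as Protocol 7.1.1 and SAP 6.0 describe and that continuing arms enrol alongside the reopened ones. It does not extend to a general failure of blinding or to the immunohistology endpoint. The documents do not say whether any trigger has occurred. The matter should be settled before any arm is reopened, because a blind lost during enrolment cannot be restored.

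**What to change.** Supply every 300 mg regimen as three active capsules plus one matching ABBV-4083 placebo capsule a day. Each arm then takes four ABBV-4083/placebo capsules whichever arms are closed: (3 + 1) × 14 = 56. The active dose in each regimen is unchanged, and with the albendazole or placebo capsule the daily total is five, within the limit in Protocol 7.3.1.2 ("Subjects will receive a maximum of 5 capsules per day for 14 days").

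Align the text:

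- Protocol 7.1.1: state the added placebo capsule at 300 mg.
- Protocol Table 1 and SAP 2.3: Arm J is no longer needed, because Arm E already matches. The SAP pools E and J for analysis in any case.
- SAP 6.0: the 300 mg denominator becomes 56 instead of 42. Treatment completion is defined in days, so the per-protocol definition is untouched.
- Protocol 7.4.1: add capsule number to the blinding measures.

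State as a limitation that this closes the capsule-count leak only: subjects of a reopened arm enrolled after the other arms have filled could still be identified by timing.

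The cost is reconfigured 300 mg kits from central packaging, the matching dispensing instructions, edits to both documents while the trial is running (57 subjects were already randomised at Amendment 1), and one more capsule a day in the 300 mg arms. The placebo capsule itself already exists (Protocol Table 2).
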